Refers to all interventional cardiology methods for treatment of coronary artery disease.

PRINCIPAL INVESTIGATOR

A physician-specialist, related to the study, who is responsible for the overall conduct of the trial at all sites and compliance with protocol and relevant.

PRIMARY INVESTIGATOR

A physician responsible for conducting the clinical trial at each investigational site.

PROCEDURE START DATE AND TIME

Procedure start date and time is recorded as the date and time the first guiding catheter was inserted into the subject.

PROCEDURE END DATE AND TIME

Procedure end date and time is recorded as the time the last guiding catheter was removed from the subject.

SUCCESSFUL PRE-DILATATION

Pre-dilatation has been successfully completed without complications if all of the following apply:

- For randomized subjects: RVD remains ≥ 2.50 mm - ≤ 3.75 mm and length of the lesion that will be covered by the device (including any edge dissections) is still ≤ 24 mm
- For Lead-In subjects: RVD remains ≥ 2.75 mm - ≤ 3.25 mm and length of the lesion that will be covered by the device (including any edge dissections) is still ≥ 8 mm - ≤ 14 mm
- Residual %DS is a maximum of $< 40\%$ (per visual estimation), $\leq 20\%$ is strongly recommended.
- TIMI Grade-3 flow (per visual estimation),
- No angiographic complications (e.g. distal embolization, side branch closure),
- No dissections NHLBI grade D-F
- No chest pain lasting > 5 minutes
- No ST depression or elevation lasting > 5 minutes.

TARGET LESION (Analysis Definition)

The target lesion is defined as the lesion that has met the angiographic inclusion and exclusion criteria in a registered subject upon calling IVRS.

Under these conditions, the lesion will be considered the target lesion regardless of the device implantation and treatment actually received.

TARGET VESSEL

The entire epicardial vessel in which the target lesion is located.

RANDOMIZED SUBJECT

Subject is considered randomized after the interactive voice response system (IVRS) has been called and a device (Absorb BVS or XIENCE) has been assigned.

REGISTERED SUBJECT

Subject is considered registered upon randomization. Lead-In subjects will be considered registered upon calling IVRS.

UNSTABLE CARDIAC ARRHYTHMIA

[figure not shown]
Any irregularity in the heart's natural rhythm associated with hemodynamic instability that has not been controlled in spite of treatment.

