	
successfully with XIENCE, the remaining target lesion(s) must be treated with Absorb BVS.
 
• In the case of two or three target lesions assigned to XIENCE, if any of the target lesions is unsuccessfully treated with XIENCE, the investigator should treat the lesion per standard of care. If the target lesion that failed treatment with XIENCE is treated successfully with standard of care, the remaining target lesion(s) must be treated with XIENCE.• For patients in whom 2 or 3 target lesions will be treated, a maximum of one staged procedure is allowed. The decision to stage may be made prior to the first intervention, or immediately after the first intervention (depending on the complexity, contrast and radiation use of the first procedure). If a staged procedure becomes necessary, it is strongly recommended that the staged procedure occurs within 2 weeks of the index procedure, but in all cases no more than 35 days from the index procedure. The assigned device must be used for staged procedures. To avoid having to cross a previously implanted study device, it is strongly recommended that the staged lesion(s) be located in a separate epicardial vessel from the lesion(s) previously treated during the first intervention.• Successful lesion treatment is defined as final diameter stenosis $\leq 30\%$ with final TIMI-3 flow, with no residual dissection NHLBI grade \geq type B, and no transient or sustained angiographic complications (e.g. distal embolization, side branch closure), no chest pain lasting > 5 minutes, and no ST segment elevation or depression lasting > 5 minutes.• For Absorb BVS, the scaffold should be deployed slowly, by pressurizing the delivery system in 2 atm increments each over 5 seconds, until the scaffold is completely expanded. Pressure should be maintained for 30 seconds if tolerated by the patient.• For the Absorb BVS and XIENCE delivery balloon, do not exceed the rated burst pressure (RBP) per the IFU for the individual device.• Post-dilatation of target lesion treated with XIENCE should be per standard of care.• Post-dilatation of the scaffold is strongly recommended for all Absorb treated lesions, especially for any implanted 2.5 mm ABSORB scaffolds. If post-dilatation of the target lesion
--	--

treated with Absorb BVS is performed the following guidance is given:

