6. SUBJECT SELECTION AND WITHDRAWAL

6.1 Subject Population

Subjects registered into this Clinical Investigation will be male and female subjects derived from the general interventional cardiology population. The Clinical Investigation will register approximately 2600 subjects, with up to three *de novo* native coronary artery lesions in a maximum of two epicardial vessels and a maximum of two lesions per epicardial vessel, who meet all eligibility criteria, have provided written Informed Consent and have been registered in the trial.

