7.5 Clinical Follow-up for All Subjects

Please see **Protocol Summary** for clinical follow-up schedule and PRO follow-up assessments.

Registered subjects must be clinically followed even if no assigned device is implanted. Clinical follow-up visits must be conducted by a blinded physician, research coordinator, Nurse Practitioner or Physician Assistant who has been trained to the protocol.

For subjects having staged procedures, the follow-up period is considered as having begun upon completion of the original index procedure.

To assess any potential perception bias on the secondary endpoint of percentage of patients who experienced angina within 1 year, information will be collected in a brief patient perception assessment questionnaire administered by the research coordinator post-procedure in the hospital prior to discharge (≥ 4 hours to ≤ 7 days after the procedure) and at 1 year.

The PRO questionnaires will be mailed to the subject for completion or can be completed during the phone or office visit. If questionnaires are mailed to the subjects, the subjects must mail the questionnaires back to the clinical site.

The following information will be collected at each of the time points:

- Any adverse events (including re-hospitalizations)*, repeat coronary angiography, details regarding angina, medications, laboratory tests and 12-lead ECGs, if performed;
- Any angina events
 - If the subject experiences any symptoms of abnormal chest/arm/neck/jaw discomfort or pain, including angina-equivalent or atypical angina pain/sensation, data will be solicited and recorded regarding angina and angina-equivalent symptoms, including the quality, frequency and severity of discomfort/pain, to allow the CEC to adjudicate the symptoms as to angina/angina-equivalent vs. non-angina. This information will be collected by the research coordinator using a standard script. A blinded cardiologist will review the information collected by the research coordinator, provide a diagnosis and sign-off on his/her diagnosis.
- Any repeat coronary angiography and results of such, if applicable;
- Details of any subsequent coronary interventions (e.g., repeat PCI or CABG);
- Use and compliance of medications per clinical investigation plan;
- Use and changes in concomitant cardiovascular medications.

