2.2.3 Other Subgroups

The following subgroups will be evaluated for the ITT population. The treatment comparisons in these analyses are not powered for hypothesis testing and are not meant for confirmatory inference. Baseline demographics, baseline subject characteristics, procedure information, morphology, quantitative coronary angiography, and hierarchical/non-hierarchical adverse event data will be summarized with descriptive statistics. Comparisons will be made between treatment arms within each of these subgroups.

Ethnicity:

- Non-white
- White

Age:

- Age \geq Median, Age $<$ Median
- Age <45 , ≥ 45 and <55 , ≥ 55 and <65 , ≥ 65 and <80 , and ≥ 80

Number of Target Lesion/Vessel Treated:

- Single target lesion/vessel treated, which includes subjects who had only one target lesion/vessel treated
- Dual target lesion/vessel treated, which includes subjects who had two target lesion/vessel treated
- Three target lesion/vessel treated, which includes subjects who had three target lesion/vessel treated.

Angina Status

- Acute coronary syndrome (unstable angina, NSTEMI, recent STEMI)

- Stable angina or silent ischemia
- Recent STEMI
- NSTEMI
- Unstable Angina
- Stable Angina
- Silent ischemia

Antiplatelet Therapy

- P2Y12 Receptor Inhibitor (Yes/No)
- Clopidogrel or Ticlopidine (Yes/No)
- Prasugrel or Ticagrelor (Yes/No)
- Clopidogrel (Yes/No)
- Ticlopidine (Yes/No)
- Prasugrel (Yes/No)Ticagrelor (Yes/No)

RVD by QCA

- $RVD \geq \text{Median}$, $RVD < \text{Median}$
- Small Vessel ($RVD \geq 2.25 \text{ mm}$, $RVD < 2.25 \text{ mm}$)

Implanted Device Diameter

- Device Diameter 2.5 mm vs. 3.0 mm vs. 3.5 mm

Population

- ABSORB III-like (Yes/No)
- ACS (Yes/No)

Implantation technique

- Compete PSP vs Incomplete PSP
 - The implantation technique used during the index procedure must satisfy all of the following criteria to be considered as complete PSP, otherwise it will be incomplete PSP
 1. Pre-dilatation performed
 2. QCA $RVD \geq 2.25 \text{ mm}$
 3. Post-dilatation performed with pressure $> 16 \text{ atm}$ and nominal scaffold diameter $<$ diameter of post-dilatation balloon \leq nominal scaffold diameter + 0.5 mm
- Each of the three individual component of complete PSP listed above (Yes/No)

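### The lesion-count subgroup is defined by target lesions actually treated, so in the ITT population membership can depend on what happens after randomization

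*SAP*

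**What the plan says.** SAP 2.2.3 introduces the list with "The following subgroups will be evaluated for the ITT population" and adds "Comparisons will be made between treatment arms within each of these subgroups". For the number of target lesions or vessels, the first two groups are "Single target lesion/vessel treated, which includes subjects who had only one target lesion/vessel treated" and "Dual target lesion/vessel treated, which includes subjects who had two target lesion/vessel treated"; a third group covers three. SAP 2.2 says the subgroup analyses are intended for the final product IFU and are run on ABSORB IV (N=2600) and on the pool with ABSORB III (N=4600). SAP 2.2.3 also says they are unpowered and not confirmatory.

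The ABSORB IV Protocol Summary (Treatment Strategy) puts a subject in the ITT population at randomization. Only one planned target lesion need have been successfully pre-dilated by then. One staged procedure is allowed for subjects with two or three target lesions, "but in all cases no more than 35 days from the index procedure". Section 7.5 of the ABSORB IV part fixes the clock: "For subjects having staged procedures, the follow-up period is considered as having begun upon completion of the original index procedure". Treatment Strategy and section 7.3.4 also allow a lesion revealed during treatment to become an unplanned target lesion if it meets the criteria.

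Appendix II, which ABSORB IV adopts for definitions it does not update, settles target-lesion status at the IVRS call; from then on "the lesion will be considered the target lesion regardless of the device implantation and treatment actually received".

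**The concern.** A subgroup factor for comparing randomized arms should be fixed at or before randomization. Here it is fixed later, by events that include the outcome being compared. To reach the dual or three-lesion group, a staged subject must survive to the second procedure. A planned two-lesion subject who dies first carries the event into the single-lesion group. If the arms differ in how often early complications curtail treatment, or in how often unplanned target lesions arise, the arms within a group no longer hold comparable patients. An IFU reader would naturally take the number of lesions as something known about the patient before treatment.

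The combined lesion/vessel label is a lesser, editorial matter. ABSORB IV enrols subjects with lesions "in a maximum of two epicardial vessels and a maximum of two lesions per epicardial vessel", so one subject can be dual by lesion and single by vessel, and a planned three-vessel group cannot occur.

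**Working it through.** The plan states no figure for this subgroup, so there is none to reproduce. The check has two parts.

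**1. Order of events in ABSORB IV.** One planned lesion is pre-dilated; the subject is randomized and enters ITT; the first target lesion is treated; the others follow in the same session or in one staged procedure by day 35. Follow-up runs from the index procedure and the primary endpoint closes at day 30, so staging can span the whole primary window. Four cases:

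- Two lesions planned, the second to be staged, cardiac death beforehand: counted as a single-lesion TLF event; two by plan.
- Three planned, stopped after two: counted as dual; three by plan.
- One planned, plus one unplanned target lesion: counted as dual; one by plan.
- No target lesion treated: no listed group applies.

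No legible text in either document classifies such subjects by plan.

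**2. Scale, illustration only.** N = 2600/2 = 1300 per arm comes from the documents. The rest is assumed:

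- share planned for more than one target lesion, m = 10–30%;
- true 30-day event risk, r = 3–5%, equal in single- and multi-lesion subjects;
- share of multi-lesion events that stop further treatment, q = 10–50%.

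Formulas per arm, with N_m = N·m and N_s = N·(1 − m):

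- moved = N_m·r·q
- single-lesion rate = (N_s·r + moved)/(N_s + moved)
- multi-lesion rate = (N_m·r − moved)/(N_m − moved)

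At m = 20% and r = 5%, N_m = 260 (13 events) and N_s = 1040 (52 events):

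| q | moved per arm | single-lesion rate | multi-lesion rate |
|---|---|---|---|
| 10% | 1.3 | 53.3/1041.3 = 5.12% | 11.7/258.7 = 4.52% |
| 30% | 3.9 | 55.9/1043.9 = 5.35% | 9.1/256.1 = 3.55% |
| 50% | 6.5 | 58.5/1046.5 = 5.59% | 6.5/253.5 = 2.56% |

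The true rate is 5% in every cell. Over the full grid, subjects moved run from 1300 × 0.10 × 0.03 × 0.10 = 0.4 to 1300 × 0.30 × 0.05 × 0.50 = 9.8 per arm. At q = 10% the range is 0.4 to 2.0.

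If q is 50% in one arm and 10% in the other, with r = 5% in both and no true difference, the multi-lesion groups differ by 2.56 − 4.52 = −1.96 points. The single-lesion groups differ by +0.21 (m = 10%) to +0.80 points (m = 30%).

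The model sends every moved subject to the single-lesion group and ignores upward moves. It shows how the mechanism works and does not estimate its size.

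**The case against.** The strongest reply is that the route is narrow. Much of it stands.

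- A reader might infer that any early infarction or thrombosis pushes a subject into the single-lesion group. The protocol does not support that. Of these events, only death necessarily ends treatment. After a failed Absorb attempt the lesion gets XIENCE, and once that succeeds the remaining target lesions are still to get the assigned device. Failed pre-dilatation of a later lesion also leads to XIENCE. Device failure alone does not lower the count.
- Periprocedural MI rests mainly on CK-MB drawn 6–12 and 18–24 hours after the procedure. In a single session the other lesions are normally treated by then. An overt complication during the procedure could still stop treatment.
- Staging is the exception. Section 4.3 asks for all target lesions to be treated at the index procedure where possible and strongly recommends staging within 2 weeks. Planned staging is not allowed in ABSORB III, so this route is weaker in the pooled tables.
- The Appendix II definition says which lesion is a target lesion, not how many were treated, so it is only indirect support.
- The same SAP list has other procedure-based groups (implanted device diameter, implantation technique), so counting lesions treated is a consistent descriptive choice.
- The randomization sections and much of the later SAP are redacted. A derivation rule or planned-lesion stratum could be there.

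What the reply does not remove is that the legible definition is post-randomization and is used to compare arms within ITT.

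**Conclusion.** The point holds as a minor one. Group membership is settled after randomization, can be lowered by death or by a complication that prevents later treatment, can be raised by an unplanned target lesion, and can differ by arm. The number affected is probably small. It cannot be derived, because the documents give no frequency of multi-lesion, staged or curtailed treatment; every illustrative figure above except N is an assumption.

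Two stronger readings should be resisted. A reader might conclude that the multi-lesion arm difference is biased by a known amount or in a known direction. The documents do not show this: q is unknown, moves go both ways, and a three-lesion subject stopped after two stays multi-lesion. A reader might also conclude that the trial's main results are at risk. They are not: the primary and powered secondary tests do not use this factor, and the SAP calls these comparisons non-confirmatory. The consequence is confined to descriptive tables, which matter because they are intended for the IFU.

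**What to change.** In SAP 2.2.3:

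- For between-arm comparisons, define the factor as the number of target lesions planned before the IVRS call (1, 2 or 3), whatever is later treated.
- State that unplanned target lesions do not change the group.
- Keep the number of target lesions treated as a descriptive tabulation, with a row for none treated.
- Tabulate lesions and vessels separately, with planned target vessels as 1 or 2.

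The cost is small but not nil. The legible text does not show that a planned count is recorded at the IVRS call, and section 4.3 refers to lesions identified at the index procedure, which is not quite the same moment. The sponsor must confirm that the count is retrievable. Some subjects with an unplanned target lesion will carry a label below the number of study devices they received; the descriptive tabulation makes this visible.

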2.3 Analysis Window

- Pre-procedure
- Post-procedure
- 30 days

- 90 days
- 180 days
- 270 days
- 1 year (365 days)
- 2 years (730 days)
- 3 years (1095 days)
- 4 years (1460 days)
- 5 years (1825 days)
- 6 years (2190 days)
- 7 years (2555 days)
- 8 years (optional, 2920 days)
- 9 years (optional, 3285 days)
- 10 years (optional, 3650 days)

[REDACTED]

[REDACTED]

[REDACTED]

[REDACTED]

[REDACTED]

[REDACTED]

[REDACTED]

[REDACTED]

[REDACTED]

[REDACTED]

[REDACTED]

[REDACTED]

[REDACTED]

[REDACTED]

[REDACTED]

[REDACTED]

[REDACTED]

[REDACTED]

[REDACTED]

[REDACTED]

[REDACTED]

[REDACTED]

[REDACTED]

[REDACTED]

[REDACTED]

[REDACTED]

[REDACTED]

[REDACTED]

[REDACTED]

[REDACTED]

[REDACTED]

[REDACTED]

[REDACTED]

[REDACTED]

[REDACTED]

[REDACTED]

[REDACTED]

[REDACTED]

[REDACTED]

[REDACTED]

[REDACTED]

[REDACTED]

[REDACTED]

[REDACTED]

2.11 Documentation and Other Considerations

All analyses will be performed using SAS® for Windows, version 9.1 or higher.

4. ACRONYMS AND ABBREVIATIONS

| Acronym/ Abbreviation | Term |
|------------------------------|--|
| ARC | Academic Research Consortium |
| AT | As-Treated |
| CEC | Clinical Events Committee |
| CK-MB | Creatine Kinase Myocardial-Band Isoenzyme |
| CVA | Cerebrovascular Accident or Stroke |
| DSMB | Data Safety Monitoring Board |
| ECG | Electrocardiogram |
| ITT | Intent To Treat |
| IVRS | Interactive Voice Response Service |
| MACE | Major Adverse Cardiac Events |
| MI | Myocardial Infarction |
| mm | Millimeter |
| NCSS/PASS | Number Cruncher Statistical System/Power Analysis and Sample Size software |
| NI | Non-inferiority |
| NSTEMI | Non-ST-segment elevation MI |
| PCI | Percutaneous Coronary Intervention |
| PMA | Pre-Marketing Approval |
| RVD | Reference Vessel Diameter |
| SAP | Statistical Analysis Plan |
| SAS | Statistical Analysis Software |
| STEMI | ST-segment elevation MI |
| TLF | Target Lesion Failure |
| TLR | Target Lesion Revascularization |
| TVF | Target Vessel Failure |
| TVR | Target Vessel Revascularization |
